### 7.3.2 Reporting a Suspected Unexpected Serious Adverse Reaction (SUSAR)

All SAEs that are 'suspected' (relationship to drug of definite, probable or possible) and 'unexpected' are to be reported to ██████ Product Safety within 24 hours after the site becomes aware of the event, via the SAE reporting process outlined above. All SAE/SUSARs will be promptly reported to the IRB/IEC and governing health authorities (eg, United State Food and Drug Administration [FDA]) as required by the IRB/IEC, federal, state, and local regulations and timelines.

## 7.4 Procedures for Unmasking of Study Drug

All subjects, investigators, and study personnel involved with the conduct of the study will be masked with regard to treatment assignments. The mask may be broken in exceptional circumstances. In a medical emergency, when the management of a subject's condition requires knowledge of the treatment assignment, the Investigator, or designee, will obtain the study treatment assignment from the Interactive Web Response System (IWRS). If possible, the medical emergency should be discussed with the Medical Monitor prior to obtaining the treatment assignment, or as soon after as possible. The Sponsor may unmask for regulatory submission determination of an SAE when necessary (see [Section 7.3.1](#)).

In a non-emergency situation, when a code break is required, it must be discussed with the Medical monitor and/or ██████ Product Safety and the study sponsor. The code break must be approved in writing by the Sponsor.

If the randomization code for a subject is broken, the Investigator will record the date and reason for lifting the mask for that subject in the source documents. Upon unmasking, the subject will be withdrawn from the study and should complete both the Early Termination and Follow-up procedures.

Study staff will examine and reconcile study medication orders, records of receipts, dispensing records, and inventory forms throughout the study (see [Section 9.5.2](#)).

## 7.5 Type and Duration of the Follow-up of Subjects after Adverse Events

The investigator will follow unresolved AEs to resolution until the subject is lost to follow-up or until the AE is otherwise classified. Resolution means the subject has returned to baseline state of health or the investigator does not expect any further improvement or worsening of the AE. If the subject is lost to follow-up, the investigator should make 3 reasonable attempts to contact the subject via telephone, post, or certified mail. All follow-up will be documented in the subject's source document. Non-serious AEs identified on the last scheduled contact must be recorded on the AE eCRF with the status noted.

If the investigator becomes aware of any new information regarding an existing SAE (i.e. resolution, change in condition, or new treatment), a new SAE Report Form must be completed and faxed to ██████ Product Safety within 24 hours of the site's awareness of the new information. The original SAE form is not to be altered, but a new SAE Report Form must be completed and identified consecutively based on the previous report form (i.e. Initial Report, Follow-up #1, Follow-up #2, etc.). The report must describe whether the event has resolved or continues and how the event was treated.

## 8 STATISTICAL HYPOTHESES AND METHODS OF ANALYSES

### 8.1 Analysis Populations

The following analysis populations will be considered:

- All Subjects – All subjects who sign the ICF
- Modified Intention-to-Treat – Modified Intention-to-Treat (mITT) includes all subjects randomly assigned to study treatment and who take at least 1 dose of study treatment. Subjects will be analyzed according to the treatment they are randomized to.
- Per Protocol Population – The Per Protocol (PP) population includes subjects in the safety population who do not have significant protocol deviations and who complete the study. Protocol deviations will be assessed prior to database lock and unmasking. The PP population will be analyzed using observed data only for efficacy variables. Subjects in the PP population will be analyzed as treated.
- Safety Population – The safety population includes all subjects who have received at least one dose of the investigational product. The safety population will be analyzed for all safety assessments. Subjects in the Safety population will be analyzed as treated.
- PK Population – The PK population includes all subjects with an evaluable PK sample. The PK population will be used to summarize all perfluorohexyloctane blood concentrations.

The statistical analysis of safety data will be performed for the safety population. The analysis of efficacy data will primarily be performed for the mITT population. The efficacy analysis based on the PP population will serve as the sensitivity analyses.

### 8.2 Statistical Hypotheses

The following two sets of hypotheses will be tested as the primary hypotheses of the study:

**H01:** The difference in the mean change from baseline to Week 8 total Corneal Fluorescein Staining (CFS) score between NOV03 QID and combined saline solution groups (NOV03 QID – combined saline solution) = 0 against

**H11:** The difference in the mean change from baseline to Week 8 total CFS score between NOV03 QID and combined saline solution groups (NOV03 QID – combined saline solution)  $\neq$  0

and

**H02:** The difference in the mean change from baseline to Week 8 total CFS score between NOV03 BID and combined saline solution groups (NOV03 BID – combined saline solution) = 0 against

**H12:** The difference in the mean change from baseline to Week 8 total CFS score between NOV03 BID and combined saline solution groups (NOV03 BID – combined saline solution)  $\neq$  0.

### 8.3 Sample Size

This study is expected to enroll 100 subjects in each of the four treatment arms, for a total of 300 randomized subjects. [REDACTED]

[REDACTED] this study has 88% power to detect a difference of 0.8 units in the change from baseline in corneal staining between an active arm and the combined control arm using a one-sided t-test at 5% level of significance. This assumes a standard deviation of 1.9 units for each arm.

### 8.4 Statistical Analysis

#### 8.4.1 General Considerations

Quantitative variables will be summarized using number of subjects (n), mean, median, standard deviation, minimum and maximum. The qualitative variables will be summarized using counts and percentages.

All summaries will be presented by treatment group, with placebo presented both pooled as well as separately for QID and BID dosing. Summaries will be provided for demographics, baseline medical history, concurrent therapies, and subject disposition.

For the purpose of summarization, medical history, concurrent therapies, and AEs will be coded to MedDRA and WHO Drug dictionaries, as appropriate.

Baseline measures are defined as the last non-missing measure prior to the initiation of randomized study treatment.

All primary [REDACTED] will be one-sided at a significance level of 0.05.

#### 8.4.2 Unit of Analysis

For efficacy endpoints, the unit of analysis will be the study eye as defined by the following:

**Study Eye:** Eyes are eligible for analysis if they meet all of the inclusion criteria. In the case that both eyes are eligible for analysis, the worst eye shall be chosen and this will be defined as the eye with worse (higher) total corneal staining at Visit 1. If the total corneal staining is the same in both eyes then the right eye will be selected as the study eye.

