## 2.2 Overall Study Design and Investigational Plan

This study is a phase 2, multi-center, randomized, double-masked, saline-controlled study to evaluate the effect of NOV03 (████perfluorohexyloctane) at two different dosing regimens on signs and symptoms of Dry Eye Disease. Approximately 300 male and female subjects of at least 18 years of age with a subject-reported history of DED in both eyes and who meet all other study eligibility criteria will be randomized, stratified by site, 2:2:1:1 to receive 1 of 4 treatments:

Treatment 1: NOV03 (████ Perfluorohexyloctane), 4 times daily (QID)

Treatment 2: NOV03 (████Perfluorohexyloctane), 2 times daily (BID)

Treatment 3: Saline (0.9% sodium chloride solution), QID

Treatment 4: Saline (0.9% sodium chloride solution), BID

Each active treatment group will be comprised of 100 subjects and each saline group will be comprised of 50 subjects such that approximately 90 evaluable subjects per active arm and 45 per saline arm complete the study. Up to 15 sites are anticipated to participate.

This study will consist of two periods: a 14-day screening period and a 57-day treatment period (See [Appendix 1](#)).

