#### 3.3 Inclusion Criteria

Subjects will be eligible to participate in this study if they **meet all** of the following criteria

- a. Male or female subjects, of age  $\geq 18$  years (inclusive) at the time of signing the informed consent form (ICF).
- b. Provide written informed consent.
- c. Have a subject reported history of Dry Eye Disease ■■■■  
■■■■
- d. Have Tear Film Break Up Time ■■■■ sec. at Visit 0 and Visit 1.
- e. Have Ocular Surface Disease Index (OSDI®) ■■■■ at Visit 0 and Visit 1.
- f. Have a Schirmer's Test I ■■■■ mm at Visit 0 and Visit 1.
- g. Have Meibomian Gland Dysfunction defined as MGD score ■■■■  
■■■■  
■■■■  
■■■■ at Visits 0 and 1.
- h. Have a total corneal fluorescein staining score of ■■■■ ■■■■ ■■■■  
■■■■  
■■■■
- i. Have at least one eye (the same eye) satisfy all criteria for d, f, g, and h above at Visit 0 and Visit 1.
- j. Be able and willing to follow instructions, including participation in all study assessments and visits.

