### **Visit 0 (Within 14 days before Visit 1): Screening**

- Informed consent / HIPAA;
- Demographic data and medical / medication history;
- Review of inclusion / exclusion criteria;
- Adverse event query;
- Blood pressure and heart rate;
- Ocular Surface Disease Index (OSDI®) questionnaire;
- Visual acuity;
- Slit-lamp biomicroscopy;
- Tear Film Break-up Time (TFBUT);
- Fluorescein staining cornea (NEI grading);
- Lissamine green staining conjunctiva (Oxford scale);
- Meibomian gland assessment (MGD score);
- Schirmer's Test I (without anesthesia), [REDACTED]  
[REDACTED]
- Intraocular pressure;
- Dilated funduscopy;
- Blood sample collected for hematology and serum chemistry, and pregnancy test (if applicable);
- Qualified subjects will be scheduled for Visit 1.

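### The primary model adjusts for one pre-treatment CFS reading (Visit 1); adding the study eye's Visit 0 reading, already collected, would probably give a modest gain in precision at almost no cost

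*Combined protocol and SAP*

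**What the plan says.** - **Primary model (Section 8.4.5).** A repeated measures model of change in total CFS, with fixed factors for treatment, site, visit and treatment by visit, one continuous baseline term, and an unstructured covariance matrix. The target is the Week 8 contrast of each NOV03 arm with pooled saline.
- **Baseline (Section 8.4.1).** "Baseline measures are defined as the last non-missing measure prior to the initiation of randomized study treatment". CFS is graded on Day 1 before dosing, so for this endpoint baseline is Visit 1.
- **Study eye (Section 8.4.2).** If both eyes are eligible, "the worst eye shall be chosen and this will be defined as the eye with worse (higher) total corneal staining at Visit 1"; a tie goes to the right eye.
- **Visit 0 (Section 6.4.1).** The screening list includes corneal fluorescein staining on the same NEI scale.
- **Eligibility (Section 3.3, criterion i).** "Have at least one eye (the same eye) satisfy all criteria for d, f, g, and h above at Visit 0 and Visit 1". Criterion h is the staining score, so every correctly enrolled subject should have a Visit 0 value for the study eye.
- **Power (Section 8.3).** "this study has 88% power to detect a difference of 0.8 units in the change from baseline in corneal staining", "using a one-sided t-test at 5% level of significance". "This assumes a standard deviation of 1.9 units for each arm".

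**The concern.** A single CFS grading carries reading error and day-to-day variation. A second grading of the same eye before randomisation usually helps to predict the Week 8 score, and whatever it adds beyond Visit 1 comes off the residual variance of the treatment contrast. The trial collects that second grading in every subject, and no visible part of the primary analysis uses it.

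The Week 2 and Week 4 visits in the model do not replace it. They are post-treatment outcomes, and with complete data they add essentially nothing to the Week 8 contrast.

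What is at stake is precision only. It matters somewhat more than usual here because Section 8.4.4 lets BID be tested only if QID is significant, so precision on QID also governs whether BID is tested. Section 1.3 says the data will be used to plan phase 3.

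**Working it through.** **1. The plan's own figure.** Inputs from Sections 8.3 and 2.2: difference 0.8, SD 1.9, one-sided 5%, and "approximately 90 evaluable subjects per active arm and 45 per saline arm complete the study", so 90 against 45 + 45 = 90.

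Standard error = 1.9 × √(2/90) = 0.2832. Then 0.8/0.2832 = 2.825, 2.825 − 1.645 = 1.180, and Φ(1.180) = 88.1% (87.9% by noncentral t). The stated 88% reproduces.

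**2. Effect of a second baseline.** The correlations are assumed, because the documents give none. If Visit 0, Visit 1 and Week 8 CFS share one correlation ρ, then

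residual variance (Visits 0 and 1) / residual variance (Visit 1 only) = (1 + 2ρ)/(1 + ρ)².

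- ρ = 0.3: 1.6/1.69 = 0.947, a fall of 5.3%
- ρ = 0.5: 2.0/2.25 = 0.889, a fall of 11.1%
- ρ = 0.7: 2.4/2.89 = 0.830, a fall of 17.0%

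**3. Power, under two readings of 1.9.**

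*Reading A:* 1.9 is the residual SD after Visit 1 adjustment. The new SD is 1.9 × √ratio.

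*Reading B:* 1.9 is the raw SD of change, as Section 8.3 reads. With equal variances, adjusting for Visit 1 alone gives 1.9 × √((1 + ρ)/2), that is 1.532, 1.645 and 1.752. Adding Visit 0 multiplies this by √ratio, giving 1.490, 1.551 and 1.596.

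| ρ | A: Visit 1 only | A: plus Visit 0 | A: n per group for 88% | B: Visit 1 only | B: plus Visit 0 |
|---|---|---|---|---|---|
| 0.3 | 88.1% | 89.6% | 90 → 85 | 96.9% | 97.5% |
| 0.5 | 88.1% | 91.2% | 90 → 80 | 94.7% | 96.5% |
| 0.7 | 88.1% | 92.7% | 90 → 75 | 92.2% | 95.7% |

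The gain is 1.5 to 4.6 points under A and 0.6 to 3.5 points under B.

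**4. Allowing for eye selection and entry cut-offs.** A two-eye simulation (subject, eye and visit-noise components) took the worse eligible eye at Visit 1. Because the real staining threshold is redacted, it applied cut-offs at both visits ranging from none to the population mean. For ρ = 0.3 / 0.5 / 0.7 the variance fell by about 2-5% / 5-10% / 10-15%, with reading A power of 88.7-89.5% / 89.6-90.9% / 90.9-92.3%. A separate two-eye simulation with other assumed variance components gave falls of 4-18%. At 18%, the reading A SD is 1.9 × √0.82 = 1.721 and power is Φ(0.8/(1.721 × 0.1491) − 1.645) = 93.0%.

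**5. The lower bound.** Take correlations of 0.6 (Visit 0 with Visit 1), 0.5 (Visit 1 with Week 8) and 0.3 (Visit 0 with Week 8). Because 0.3 = 0.6 × 0.5, Visit 0 informs Week 8 only through Visit 1. Two-predictor R² = (0.25 + 0.09 − 2 × 0.5 × 0.3 × 0.6)/(1 − 0.36) = 0.16/0.64 = 0.25, the same as Visit 1 alone (0.5² = 0.25). The gain is zero. If the third correlation is 0.4, R² = 0.17/0.64 = 0.2656, the ratio is 0.7344/0.75 = 0.979, and reading A power is 88.7%.

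**6. Is the worse-eye rule the cause?** Worse-eye selection was simulated against taking the first eligible eye, under three assumed variance sets. The correlation of baseline with Week 8 was 0.46 v 0.44, 0.66 v 0.65 and 0.80 v 0.80 without a cut-off, and 0.30 v 0.26, 0.47 v 0.41 and 0.64 v 0.59 with one. Residual variance after Visit 1 adjustment was lower under worse-eye selection (for example 3.52 v 3.61). The rule does not cost precision.

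**The case against.** The best defence is that nothing here is wrong. One last-pre-dose baseline in a repeated measures model is standard and valid, no passage contradicts another, and type I error, estimand and bias are untouched. The size of the gain rests wholly on assumed correlations and can be zero. Section 6.2 stops dry eye products only 24 hours before Visit 1, so Visit 0 may be read under different conditions and carry less extra information. All of this stands. It limits the point to an optional improvement but does not remove it, because a pre-randomisation covariate cannot bias the contrast and the data are already in hand.

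Three stronger readings are tempting, and the documents do not support them.

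- **The worse-eye rule makes Visit 1 CFS a poor covariate.** Picking the higher reading does favour upward error, but step 6 shows an equal or higher correlation with Week 8 and a smaller residual variance. The selection also applies only when both eyes qualify.
- **Regression to the mean threatens the 0.8-unit target.** The 0.8 is a difference between arms. Regression to the mean is a drift within arms, equal in expectation across randomised arms, so it cancels in the contrast. With an entry cut-off, most of it came from the cut-off (0.79 of 0.99, 0.49 of 0.71 and 0.26 of 0.43 units in three assumed settings), and a second covariate does not remove it. The plan's hypotheses concern contrasts with saline.
- **Power is 88% now and would become a definite higher figure.** Section 8.3 describes a t-test on change and does not call 1.9 an adjusted SD. Under reading B the planned model already exceeds 88%.

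Parts of Sections 8.4.3 and 8.4.5 are redacted, and some sensitivity analyses are left to a later SAP, so use of Visit 0 CFS elsewhere cannot be excluded. The primary model itself is fully legible.

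**Conclusion.** The point holds as a missed, low-cost efficiency gain and as nothing more. The planned primary analysis is valid and unbiased. Adding the study eye's Visit 0 CFS would lower Week 8 residual variance by roughly 2-18% under the assumed correlations and variance components, and by nothing if Visit 0 has no link to Week 8 beyond Visit 1. Where there is a gain, it is worth roughly 1-5 points of power. The starting level is 88% if 1.9 is the SD after Visit 1 adjustment, or about 92-97% (for ρ of 0.7 down to 0.3) if it is the raw SD of change. Priority is low.

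**What to change.** In Section 8.4.5, add the study eye's Visit 0 total CFS as a second continuous covariate beside the Visit 1 baseline, and fix this in writing before unmasking. Leave the Section 8.4.2 study-eye rule and the Section 8.4.1 definition of baseline as they are, so that change is still measured from Visit 1. For a rescreened subject, state that Visit 0 means the screening visit of the successful attempt.

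The cost is one degree of freedom and a sentence of text. No new data, visits or subjects are needed, and the endpoint and estimand do not change. It would also help to state in Section 8.3 whether 1.9 is a raw or an adjusted SD, since that decides the power from which the gain is counted.

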#### 8.4.3 Missing Data

The primary efficacy analyses will be performed using the mITT population, and using a repeated measures model without any imputation for missing observations. Sensitivity analyses using different analysis populations and methods for handling missing data may be further detailed in the Statistical Analysis Plan (SAP).

[REDACTED]

#### 8.4.4 Multiplicity Consideration

To control for inflation of type 1 error rate due to multiple hypotheses, the analysis will be conducted in a hierarchical manner.

The hypothesis testing to compare the BID arm and control will only proceed if the QID vs. control comparisons are statistically significant.

#### 8.4.5 Primary Efficacy Analyses

All efficacy analyses will be primarily based on the mITT. Population. Analyses based on Per-Protocol (PP) population will be supportive in nature. The primary evaluation of efficacy of the active arms will be against a combined control arm (with BID and QID saline solution). Analyses will also be provided comparing BID to QID saline solution to determine appropriateness of combining for the primary analysis. Sensitivity analysis may be undertaken for dosing-regimen matching control (that is, QID active vs. QID saline solution).

The primary analysis will be performed to compare the Week 8 difference in the change from baseline in total CFS between each of the active NOV03 groups and the combined saline solution group. The comparison will be conducted using a repeated measures model with treatment, site, visit, and treatment by visit interaction as fixed categorical factors, baseline as a continuous covariate, and using an unstructured covariance matrix. To establish evidence of efficacy in this proof of concept study, the hypothesis tests will be one-sided and performed at the 0.05 significance level.

The total CFS score is calculated as the sum of the staining from the inferior, central, superior, nasal, and temporal regions, such that a larger number indicates worse dry eye signs.

Treatment group contrasts and least-squared (LS) means will be presented from the model together with two-sided 95% confidence intervals.

The primary analysis will use the mITT population at the Visit 4, Week 8 visit; the PP population will also be used to further understand the primary results.

[REDACTED]

- [REDACTED]
- [REDACTED]
- [REDACTED]
- [REDACTED]
- [REDACTED]
- [REDACTED]
- [REDACTED]
- [REDACTED]
- [REDACTED]
- [REDACTED]
- [REDACTED]
- [REDACTED]
- [REDACTED]
- [REDACTED]

[REDACTED]

[REDACTED]

[REDACTED]

[REDACTED]

[REDACTED]

[REDACTED]

[REDACTED]

[REDACTED]

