	
[REDACTED]

Safety Endpoints:	

• Visual Acuity.

• Slit-Lamp Biomicroscopy.

• Intraocular Pressure.

• Dilated Fundoscopy.

• Hematology/Chemistry parameters.

• Systemic and ocular adverse events.

• Symptoms directly related to the instillation or use of the investigational medication based on questionnaire/visual analogue scale.

Other:	

• Pharmacokinetics of perfluorohexyloctane (blood levels for perfluorohexyloctane at predefined time points and PK parameters as appropriate).

General Statistical Methods and Types of Analyses
 
Sample Size At least 300 subjects (100 each for the two active arms, and 50 each for the two saline solution arms) will be randomly assigned to study treatment such that approximately 90 evaluable participants per active arm and 45 per saline solution arm complete the study, assuming a 10% dropout rate.
 
Primary Efficacy Analyses: The primary evaluation of efficacy of the active arms will be against a combined control arm (with BID and QID saline solution). Sensitivity analysis may be undertaken for dosing-regimen matching control (that is, QID active vs. QID saline solution). The primary analysis will be performed to compare the week 8 difference in the change from baseline in CFS between the active NOV03 groups and the saline solution groups. The comparison will be conducted using a repeated measures model with treatment, site, visit, and treatment by visit interaction fixed categorical factors, baseline as a continuous covariate, and using an unstructured covariance matrix. To establish evidence of efficacy in this proof of concept study, the hypothesis tests will be one-sided and performed at the 0.05 significance level.
 
[REDACTED]
 
[REDACTED]
 
[REDACTED]
 
[REDACTED]
	

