### **Visits 2-4**

Subjects will return to the clinic on Day 15±1 (Visit 2), 29±2 (Visit 3), and 57±2 (Visit 4) to be evaluated for signs and symptoms of dry eye disease. During this period, subjects will dose NOV03 or the saline solution QID and BID, depending on their assigned group. The unused portion of the study medication should be returned to the clinic and a new study medication kit will be dispensed. The diary will be checked. At Visit 4, vital signs will be evaluated and a second blood draw will be performed for PK at selected sites. The diary will be collected at the clinic during each visit. Subjects will be dismissed from the study after all Visit 4 assessments have been completed.

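### The primary repeated measures model fits one baseline slope across Weeks 2, 4 and 8; a baseline-by-visit term would protect Week 8 precision at almost no cost

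*Combined protocol and SAP*

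**What the plan says.** Section 8.4.5 sets out the primary analysis: the Week 8 change in total CFS is compared between each active arm and the pooled saline arms. The model's fixed factors are treatment, site, visit and the treatment-by-visit interaction; the rest of its specification reads "baseline as a continuous covariate, and using an unstructured covariance matrix". The synopsis gives the same list: "repeated measures model with treatment, site, visit, and treatment by visit interaction fixed categorical factors, baseline as a continuous covariate". The post-baseline visits are Days 15, 29 and 57 (Section 2.4), that is, Weeks 2, 4 and 8.

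So the treatment effect may differ at each visit and the covariance is unrestricted, but baseline enters once, as a main effect. No visible text adds a baseline-by-visit term. Parts of Section 8.4 are redacted, and Section 8.4.3 refers to a SAP for sensitivity analyses whose text is not in the document supplied. The model sentence itself is not redacted and reads as a complete list of terms.

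The power statement in Section 8.3 is separate from this model. For each active arm against pooled saline it claims "88% power to detect a difference of 0.8 units in the change from baseline in corneal staining". The calculation is described as "using a one-sided t-test at 5% level of significance". On variability, the section adds: "This assumes a standard deviation of 1.9 units for each arm".

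**The concern.** A reading taken eight weeks after baseline may relate to baseline differently from one taken at two weeks. If it does, a single coefficient is a compromise across visits, and the Week 8 comparison is adjusted with a slope that is not the Week 8 slope. The unstructured covariance does not repair this; it absorbs the misfit as extra residual variance. What is at stake is some precision in the two contrasts tested in sequence under Section 8.4.4. It can be recovered with data already collected.

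**Working it through.** **1. The plan's own figure.** Inputs: difference 0.8, SD 1.9, one-sided 5% (Section 8.3); 90 evaluable per active arm and 45 + 45 = 90 combined saline (synopsis). The standard error is 1.9 × √(2/90) = 0.283, and 0.8/0.283 = 2.82. Power is Φ(2.82 − 1.645) = 88.1%, or 87.9% with the t distribution. The stated 88% reproduces. It uses an unadjusted SD, so it takes no credit for baseline adjustment.

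**2. The mechanism.** Let b hold the three visit slopes of change on baseline, b8 be the Week 8 slope, and S be the residual covariance. With complete data the common slope tends to

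c = (1′S⁻¹b) / (1′S⁻¹1).

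The Week 8 variance per subject then rises from s8² to s8² + (b8 − c)² × Var(baseline). The relevant gap is between the Week 8 slope and the pooled slope. It is normally smaller than the whole drift from Week 2 to Week 8, and the loss is zero when b8 = c.

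**3. Size.** The documents give no baseline SD, visit slopes or within-subject correlations, so these are assumptions. The Week 8 SD of change is held at 1.9, giving s8² = 1.9² − b8² × Var(baseline), with 90 v 90 and normal-approximation power. With equal residual SDs at the three visits (compound symmetry 0.5 or autoregressive 0.7), c = −0.30 for both drifting patterns below.

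| Slopes, Weeks 2/4/8 | Baseline SD | s8² | Added variance | Inflation | Power: by-visit → common slope |
|---|---|---|---|---|---|
| −0.3/−0.3/−0.3 | any | – | 0 | 0% | no change |
| −0.2/−0.3/−0.4 | 1.5 | 3.25 | 0.0225 | 0.69% | 90.86 → 90.69% |
| −0.2/−0.3/−0.4 | 2.0 | 2.97 | 0.04 | 1.35% | 92.91 → 92.62% |
| −0.2/−0.3/−0.4 | 2.5 | 2.61 | 0.0625 | 2.39% | 95.32 → 94.93% |
| −0.1/−0.3/−0.5 | 1.5 | 3.05 | 0.09 | 2.95% | 92.35 → 91.70% |
| −0.1/−0.3/−0.5 | 2.0 | 2.61 | 0.16 | 6.13% | 95.32 → 94.29% |
| −0.1/−0.3/−0.5 | 2.5 | 2.05 | 0.25 | 12.21% | 98.24 → 97.10% |

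For example, at baseline SD 2.0 and Week 8 slope −0.4: s8² = 3.61 − 0.16 × 4 = 2.97, the added variance is 0.1² × 4 = 0.04, and 0.04/2.97 = 1.35%.

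The covariance shape matters. If residual SDs rise over the visits in the ratio 0.8 : 0.9 : 1.0 with correlation 0.7, the pooled slope is pulled towards Week 2 (c = −0.237 and −0.174). Inflation is then 1.8–6.4% for the drift of 0.2 and 7.9–32.5% for the drift of 0.4, with power losses of 0.5–1.1 and 1.8–3.6 points. These are the least favourable cases tried.

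**4. Simulation.** With 300 subjects, 10% monotone dropout, baseline SD 2.0, no site term and 1,500 trials, the empirical standard errors (common slope v by-visit) were:
- drift 0.2: 0.2566 v 0.2561, a variance ratio of (0.2566/0.2561)² = 1.004; power 93.3% v 93.5%;
- drift 0.4: 0.249 v 0.240, a variance ratio of 1.08; power 93.6% v 94.8%.

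Estimates were −0.79 to −0.80 for a true −0.80, and model standard errors tracked the empirical ones. With equal slopes, adding the term cost almost nothing (standard errors of 0.269 and 0.268 for the two models).

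**The case against.** The strongest reply is that nothing is wrong. Baseline as a main effect in a randomised, pre-specified repeated measures model is valid, and the synopsis and Section 8.4.5 agree. The documents contain no evidence that the slope drifts, and without drift the gain is zero. Entry also requires a qualifying staining score (Section 3.3, criterion h, cut-off redacted), which may narrow the baseline range and shrink any loss. In every scenario tried, including slopes that weaken over time, the common-slope model kept at least 88.3% power, above the planned 88%.

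All of that stands. It limits the point to an optional refinement but does not remove it, because the term costs almost nothing when it is not needed.

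A reader might infer four stronger things that the documents do not support:
- **That the primary estimate is biased.** Both models were unbiased when dropout was unrelated to baseline. A shift appeared only under an adverse assumption: 10% dropout depending on baseline in opposite directions in the two arms, by 6 percentage points per baseline SD. A true −0.80 then became −0.84 (drift 0.2) or −0.88 (drift 0.4) with the common slope, and −0.80 or −0.81 with the extra term. Nothing in the documents suggests that pattern.
- **That the model departs from the hypotheses.** Section 8.2 states differences in mean change at Week 8 and names no covariate. Both models estimate that difference.
- **That choosing the worse eye makes the slope drift.** The rule in Section 8.4.2 applies only when both eyes qualify. It acts once, before all post-baseline visits, so it does not by itself create drift between them.
- **That the trial is underpowered.** Section 8.3 rests on a t-test with an unadjusted SD, so this point leaves it untouched.

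**Conclusion.** The point holds as a conditional matter of efficiency. As written, the model applies one baseline slope to three visits, and the two Week 8 contrasts lose precision whenever the Week 8 slope differs from the pooled slope. With equal residual SDs and a baseline SD of 1.5 to 2.5, the variance inflation is 0% with no drift, about 1–2% for a drift of 0.2, and about 3–12% for a drift from −0.1 to −0.5. Larger losses need both strong drift and residual variance that grows over the visits. For modest drift the cost is roughly 0 to 1 power point. Under ordinary dropout, validity is not affected. The slopes, baseline SD and correlations are all assumed, so the actual gain in this trial is unknown and may be nil.

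**What to change.** In Section 8.4.5 and the synopsis, list the fixed effects as treatment, site, visit, treatment-by-visit, baseline and baseline-by-visit, and keep the unstructured covariance. If the separate SAP already contains the interaction, align the protocol wording with it.

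This is a free improvement. It uses data already collected and replaces one slope with three, which costs two degrees of freedom against about 270 evaluable subjects (90 + 90 + 45 + 45). It should be made before unmasking; adding the term to the primary model afterwards would be a post hoc choice.
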